Recent use of psychoactive medications, as determined by investigators
Otherwise determined by investigator to be unfit for participation:
ex) meets DSM criteria for current alcohol or substance use disorder (in last 3 months)

**Investigational
Product (drug,
biologic, device, etc.)**

**For Device include
the planned use**

MagVenture X100 Stimulator - *please refer to the 'Devices in Research Form' attached to this submission*

**For Drug, food,
cosmetic, etc.**

MagVenture Cool B65 Coil - *please refer to the 'Devices in Research Form' attached to this submission*

include the dose,

route of

administration and

dose regimen

MagVenture MRI B91 Coil - *please refer to the 'Devices in Research Form' attached to this submission*

CONFIDENTIAL

This material is the property of the University of Pennsylvania.

Duration of administration (if applicable)	The neuromodulation participants will receive is FDA-approved iTBS at 120% RMT stimulation intensity; triplet 50 Hz bursts, repeated at 5 Hz; 2 s on and 8 s off; 600 pulses per session; for a total duration of 3 min 9 s per session to the 'Fitzgerald Target' (identified via MRI imaging). Sham TMS will also be administered at the aforementioned parameters.
Reference therapy	When in the scanner, participants will receive single pulse TMS probes while completing tasks at 120% RMT with 77 total pulses.
Statistical Methodology	Efficacy within subjects: Repeated measures ANOVA will be used to assess changes from baseline to post-stimulation for each task condition. Efficacy between subjects: neuro-response rates and time to response will be compared with published rates within the literature to extrapolate the significance of this modality.
Safety Evaluations	No data or safety monitoring board will be necessary for this protocol. The principal investigator will be responsible for monitoring this protocol.
Data and Safety Monitoring Plan	No data or safety monitoring board will be necessary for this protocol. The principal investigator will be responsible for monitoring this protocol.

CONFIDENTIAL

This material is the property of the University of Pennsylvania.

BACKGROUND AND STUDY RATIONALE

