3.1 Primary Objective

We will determine both an “intensity (difficulty) effect” and an “emotion effect” of task-induced fMRI activity in the scanner, collecting these measures in the same subjects. Participants will receive two working memory tasks:

1a) Sternberg Sorting Task (SST): a cognitive task comparing low-load vs. high-load conditions in which the picture stimuli are letters.

1b) International Affective Picture System (IAPS): an emotional task using IAPS picture that will also compare low load and high load conditions. The number of images will vary by condition load, but for both the high-load & low-load conditions, participants will look at IAPS pictures and answer questions about the images. Further, jittered within this design will be both neutral and negative blocks of IAPS pictures.

We will compare low-load vs. high-load brain activation and connectivity in the cognitive vs. emotional tasks.

Hypothesis 1a: Compared with the maintenance (low-load) SST condition, the high-load cognitive SST condition will produce greater DLPFC activation and dIPFC/sgACC anticorrelation.

Hypothesis 1b: Compared with the low-load IAPS emotional task, the high-load IAPS emotional pictures will produce higher activity in the DLPFC and dIPFC/sgACC anticorrelation.

Hypothesis 1c: The picture rating for arousal will be correlated with the activity in the DLPFC and dIPFC/sgACC anticorrelation.

Secondary Objectives:

Aim 2: to determine which task provides greater augmentation of the TMS-induced DLPFC activation, participants will receive in randomized order:

- 1) The cognitive SST working memory task or the IAPS task alone
- 2) rTMS + the cognitive SST working memory task or rTMS + the IAPS emotional task in randomized order. rTMS and the cognitive tasks will be conducted in the fMRI scanner where brain activation to a TMS probe and connectivity will be obtained.
- 3) rTMS alone

Hypothesis 2a: rTMS + either task will have greater DLPFC activation and greater dIPFC/sgACC anticorrelation than rTMS alone.

Hypothesis 2b: rTMS + the IAPS emotional working memory task will have greater DLPFC activation and greater dIPFC/sgACC anticorrelation than rTMS + cognitive SST (more robust)

Hypothesis 2c: rTMS + IAPS emotional task will have greater signal to noise (more selective).

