Aim 3: to determine the effect of neuromodulation on DLPFC activation healthy participants will be randomized to one of the 3 task conditions: high-load cognitive SST, high-load IAPS task, or low-load SST (sham task condition). Following a 4 session course (2 session separated by at least 4 hours on one day, followed by 2 sessions separated by at least 4 hours on a second day) of either active rTMS or sham TMS neuromodulation in combination with the task condition participants will again have probe sessions in the scanner where DLPFC activation and connectivity will be determined. Following a 2-week interval, participants will receive the other stimulation condition (sham TMS if active first and active TMS if sham first).

[figure not shown]
Hypothesis 3a: Task (any of the 3) + active rTMS will result in greater DLPFC activation and greater dIPFC/sgACC anticorrelation than task plus sham rTMS

Hypothesis 3b: the IAPS task in combination with active rTMS will produce greater activation than the cognitive SST + active TMS or than control task + active TMS.

CONFIDENTIAL

4 Investigational Plan

Below is an example of the proposed study flow after screening visit. Please refer to attached task descriptions for further information:

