6.2 Study Intervention Phase

6.2.1 MRI Visits

- Verify & sign MRI Safety Screening Form
- Undergo MRI with tasks
 - Baseline MRI – tasks in the scanner, no TMS probe
 - Visit 1 – tasks in the scanner with TMS

6.2.2 Prior to Baseline MRI – Randomized order of learning all 3 study tasks (SST, IAPS, and Sham) in the scanner without TMS.

6.2.3 Visit 1 – in the scanner participant completes all 3 tasks, in previously randomized order with TMS.

6.2.4 After Visit 1 – Randomized to SST task only, IAPS task only, or Sham task only & either Active rTMS + task or Sham rTMS + task

5.2.5 Neuromodulation & MRI Probe Visits:

- Visits 2 & 3: Complete randomized task alone & again with randomized rTMS group
 - Confidence rating
- Visits 4 & 5: Complete randomized task alone & again with opposite rTMS group
 - Confidence rating
- MRI probes: in the scanner, participant completes randomized task alone & then with TMS probe.

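### Hypothesis 3b compares activation levels between groups that are scanned on different tasks, so as worded it can be met by the in-scanner task alone; it should be restated as a task-group by stimulation interaction

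*Combined protocol and SAP*

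**What the plan says.** Aim 3 (section 3.1) randomises participants between three tasks: high-load SST, high-load IAPS, and low-load SST as the sham task. The task stays fixed for each person while active and sham stimulation cross over.

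The outcome scans are described in section 6.2, under the item numbered 5.2.5: "MRI probes: in the scanner, participant completes randomized task alone & then with TMS probe". The Study Summary confirms that the probe is given during task performance: "participants will receive single pulse TMS probes while completing tasks at 120% RMT with 77 total pulses".

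Hypothesis 3b states that "the IAPS task in combination with active rTMS will produce greater activation than the cognitive SST + active TMS or than control task", the last comparator also being combined with active TMS. It names no change from baseline, no subtraction of sham and no interaction.

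Two other hypotheses in section 3.1 concern the same tasks before any stimulation course. H1a expects that "the high-load cognitive SST condition will produce greater DLPFC activation and dIPFC/sgACC anticorrelation", relative to low-load SST. H2b expects IAPS to exceed SST when TMS is given in the scanner.

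Section 8 has two sentences on analysis. One is a repeated measures ANOVA of change from baseline to after stimulation, for each task condition. The other is a between-subject comparison of response rates and time to response with published rates.

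**The concern.** The task paired with the stimulation course and the task performed during measurement are the same variable. H3b compares people scanned on IAPS with people scanned on high-load or low-load SST. If the tasks themselves drive DLPFC to different levels, as the protocol predicts, the groups will differ at the outcome scan whether or not the course did anything.

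H3b is the only hypothesis that asks whether the choice of paired task changes the after-effect of neuromodulation, which is one of the study's stated objectives. If it is tested as worded, a positive result could not be read as task-specific augmentation.

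**Working it through.** The plan gives no alpha, power, SD or fMRI effect size, so there is no figure of its own to reproduce. The check has four steps.

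**1. The passages side by side**

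| Item | Source | Content |
|---|---|---|
| Who differs | 3.1, Aim 3 | Task varies between people and is fixed within a person |
| What is done at the outcome scan | 6.2 (item 5.2.5) | The person's own task, alone and then with the probe |
| What H3b compares | 3.1 | Activation level under active TMS, IAPS against each other group |
| Task difference expected without a course | 3.1, H1a and H2b | High-load SST above low-load SST; IAPS above SST with in-scanner TMS |
| Between-group analysis | 8 | Against published rates only |

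The direction predicted by H1a and H2b is the direction in which H3b would be declared met.

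**2. Size for a level comparison**

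Assumptions not in the documents: equal split, two-sided 5%, neuromodulation effect zero, and an acute task difference of *d* SD between the two groups. With 25 people, 25/3 = 8.3, so about 8 per group. For a two-sample t-test with n = 8 per group:

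- degrees of freedom = 8 + 8 − 2 = 14, critical value 2.145
- noncentrality = d × √(n/2) = d × √4 = 2d
- P(significant) = P(|T| > 2.145), with T noncentral t

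| Task difference (SD) | Noncentrality | Exact, 8 v 8 | Simulated, 9 v 8 (4,000 runs) |
|---|---|---|---|
| 0 | 0 | 5% | 4.5% |
| 0.5 | 1.0 | 15% | 16% |
| 0.8 | 1.6 | 32% | 35% |
| 1.0 | 2.0 | 46% | 50% |
| 1.5 | 3.0 | 80% | 83% |

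The simulation is slightly higher mainly because one group has 9.

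**3. The same data with a differenced contrast**

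In the same simulation (within-person correlation 0.5, additive task offset, neuromodulation effect zero), the between-group test rejects as follows.

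| Task difference (SD) | Active minus sham | Change from same-task baseline |
|---|---|---|
| 0.5 | 5.4% | 4.5% |
| 0.8 | 4.9% | 5.0% |
| 1.0 | 5.4% | 5.0% |
| 1.5 | 5.0% | 5.1% |

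The simulation standard error at 5% is √(0.05 × 0.95 / 4,000) = 0.34 percentage points, so all eight values are consistent with 5%. An additive offset cancels because it is present in both scans of the same person.

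**4. What differencing does not remove**

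Suppose the task multiplies the probe response. Let the true active-minus-sham effect be *e* in the weaker-task group and *g* × *e* in the stronger-task group, with the SD of the active-minus-sham difference equal to 1. The spurious group difference is e(g − 1). For e = 0.8 and g = 1.5 it is 0.4, and with 8 per group the test rejects in about 12% of trials. For g = 2 it is 0.8, and the test rejects in about 32%. If e = 0 the spurious difference is zero for any *g*, and the rate stays at 5%.

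**The case against.** **The percentages describe an analysis the plan does not spell out.** The one stated method for these data is a repeated measures ANOVA on change from baseline, and step 3 shows that comparing groups on change would bring the error back to 5%. This is the strongest reply, and part of it stands: the problem lies in the contrast and not in missing data. It does not dispose of the point. Section 8 runs the ANOVA for each task condition, does not link it to H3b, and has no comparison between the randomised task groups.

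**A reader might infer that training and measurement effects cannot be separated at all.** The documents do not support that. Each person has active and sham scans on the same task, and section 6.2.3 has all three tasks scanned with TMS before the course.

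**A reader might also infer that even active-minus-sham can show a group difference with no neuromodulation effect, because tasks may amplify the probe response.** Step 4 shows otherwise: amplification needs a real effect to act on. The distortion is also modest unless amplification is strong. With true effects of 0.3 to 0.8 SD it gives about 5–7% at a gain of 1.25, 6–12% at 1.5 and 9–32% at 2.

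**Scanning people on the trained task is a defensible choice.** The protocol's idea is that pairing task and stimulation augments cortical response, and a probe without a task might miss task-dependent effects. This stands, and it is a reason to change the contrast and keep the scan as it is.

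**The full run list is not visible.** The study-flow figure is not shown, and the task descriptions are in an attachment. A run common to all groups may exist there, but the text describes none after the course.

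**Conclusion.** H3b as worded is confounded with the task performed at the outcome scan, and section 8 does not correct it. For a comparison of levels after the active course with no neuromodulation effect, the chance of a significant result is about 15% to 80% for assumed task differences of 0.5 to 1.5 SD, against 5% intended. These figures rest on 8 per group, a two-sided 5% t-test and assumed task effects. The protocol gives the predicted direction but no size.

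The scope is one secondary hypothesis. H3a compares active with sham in the same person on the same task and is unaffected, as are Aims 1 and 2. Planned data can remove the additive part of the bias. What then remains is a limit on interpretation: if the task multiplies the probe response, equal plasticity would look larger in the group scanned on the stronger task.

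**What to change.** 1. Restate H3b in section 3.1, and add it to section 8, as the task-group by stimulation interaction: the between-group difference in active-minus-sham DLPFC activation and dlPFC/sgACC connectivity, for IAPS against high-load SST and against low-load SST.

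2. Express each arm of that difference as change from the same-task pre-course probe scan where one is available, and say which scan that is. If both arms use a single pre-course scan it cancels: (active − baseline) − (sham − baseline) = active − sham. Baselines matter for this contrast only if each period has its own. Section 5 lists a scan before Visit 6, but the procedures table in section 6 does not, and visit numbers differ again in section 6.2. These need to be reconciled.

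3. State as a limitation that a task which multiplies the probe response can still make equal plasticity look unequal.

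4. Reconcile section 3.1 (Aim 2), section 4.1 and the opening of section 6, which list rTMS alone, with section 6.2.3, which lists only the three tasks with TMS. If a TMS-alone run is already collected at the probe scans, use it as a sensitivity analysis under a condition common to all groups. I do not propose adding such a run: it would change the stimulation exposure, and section 6.2.3 lists no pre-course value for it.

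The cost is a few sentences and no new data. The downside is precision. With within-person correlation ρ, the active-minus-sham SD is √(2(1 − ρ)) times the single-scan SD. This is equal to it at ρ = 0.5 and larger below that. With a separate baseline in each period, and the same correlation between all scans, it becomes √(4(1 − ρ)), or 1.41 times at ρ = 0.5.

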6.3 Follow Up Phase of the Study – N/A

6.4 Unscheduled Visits

Unscheduled visits will be handled only if deemed necessary by study staff, for instance a participant presented to the ER during study participation, study staff may request the patient come in between visits for evaluation.

6.5 Subject Withdrawal

Participants may be withdrawn from the study by staff if deemed necessary for their health or safety. We anticipate that some participants may withdraw. We do not expect early termination of participation due to patient or investigator withdrawal to have any impact on safety or well-being of participants.

6.5.1 Data Collection and Follow-up for Withdrawn Subjects

N/A

6.6 Early Termination Visits

If deemed necessary to terminate a patient's participation in the study, they will be contacted by study staff to communicate this and the reason why. No other information will be collected from the terminated participant.

7 Study Evaluations and Measurements

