9.2 Recording of Adverse Events

At each contact with the subject, the investigator will seek information on adverse events by specific questioning and, as appropriate, by examination. Information on all adverse events will be recorded immediately in the source document, and also in the appropriate adverse event module of the case report form (CRF). All clearly related signs, symptoms, and abnormal diagnostic procedures results should be recorded in the source document, though should be grouped under one diagnosis.

All adverse events occurring during the study period will be recorded. The clinical course of each event will be followed until resolution, stabilization, or until it has been determined that the study intervention or participation is not the cause. Serious adverse events that are still ongoing at the end of the study period will be followed up to determine the final outcome. Any serious adverse event that occurs after the study period and is considered to be possibly related to the study intervention or study participation will be recorded and reported immediately.

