9.3 Relationship of AE to Study

The relationship of each adverse event to the study procedures will be determined by the PI and co-PI and relationships will be classified as either: definitely related, probably related, possibly related, unlikely or unrelated.

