9.4.1 Follow-up report

If an SAE has not resolved at the time of the initial report, follow-up reports with all relevant new, or reassessed, information will be submitted to the IRB until the SAE resolves or stabilizes.

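### Section 6.6 stops all further information from a terminated participant, while section 9.2 requires adverse-event questioning at every contact and follow-up of open events, and neither makes an exception

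*Combined protocol and SAP*

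**What the plan says.** Section 6.6 (Early Termination Visits) covers the case where a participant's involvement has to be ended. It says that "they will be contacted by study staff to communicate this and the reason why", and then: "No other information will be collected from the terminated participant". No exception for safety information is given.

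Section 9.2 (Recording of Adverse Events) sets four duties that bear on the same person:

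- Questioning: "At each contact with the subject, the investigator will seek information on adverse events by specific questioning and, as appropriate, by examination".
- Follow-up of every event: "The clinical course of each event will be followed until resolution, stabilization, or until it has been determined that the study intervention" or participation is found not to be the cause.
- Follow-up of open serious events: "Serious adverse events that are still ongoing at the end of the study period will be followed up to determine the final outcome".
- Later serious events: "Any serious adverse event that occurs after the study period and is considered to be possibly related to the study intervention or study participation" must be recorded and reported at once.

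Section 9.4.1 adds that, for a serious event unresolved at the first report, "follow-up reports with all relevant new, or reassessed, information will be submitted to the IRB until the SAE resolves or stabilizes".

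Section 6.5 lets staff withdraw a participant for health or safety and expects some withdrawals. Section 6.5.1, on data collection and follow-up for withdrawn subjects, contains only N/A.

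**The concern.** The two sections give staff opposite instructions about the same person. Termination is not among the endpoints at which 9.2 lets follow-up of an event stop, and the call or meeting that 6.6 prescribes is itself a contact with the subject.

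What is at stake is safety data. Events known before termination should already be on file, because 9.2 requires immediate recording. A site that followed 6.6 to the letter would still lose two things: the later course and outcome of any event still open, and any unreported event that questioning at the termination contact would have brought out. The loss would fall on a group that includes people withdrawn for their own health or safety, in whom an open event is plausible.

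**Working it through.** The point rests on no alpha, power, effect size or rate, so there is no plan figure to reproduce. The check sets 6.6 beside 9.2 under each reasonable reading of the 6.6 sentence.

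**Inputs.** The 6.6 prohibition and the 6.6 contact; from 9.2, the questioning duty and two follow-up duties (each event to an endpoint, ongoing serious events to final outcome); the planned sample of 25 from 5.5.

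| Reading of 6.6 | 9.2 follow-up duties blocked for events open at termination | 9.2 questioning at the termination contact |
|---|---|---|
| Literal: nothing further from the participant | 2 of 2 | blocked |
| Termination contact only | 0 of 2 | blocked |
| No exit assessment only | 0 of 2 | not blocked |

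**Limits on the first row.**

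- 6.6 restricts what is collected from the participant. The follow-up duties are blocked only so far as they need that source.
- One endpoint in 9.2, a finding that the study is not the cause, can be reached without the participant: under 9.3, "The relationship of each adverse event to the study procedures will be determined by the PI and co-PI", who could work from existing records.
- The 9.4.1 reports and the duty on later serious events are restricted only in part, because reassessed or volunteered information remains. They are not counted.
- The duty to record all events in the study period is not counted either, since the protocol does not define that period. If termination ended it, recording of new non-serious events might lapse, but follow-up of events already open would not.

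**Does another section settle it?** No. Section 6.5.1 is N/A, which neither prohibits nor permits anything. The follow-up phase (6.3) and medical record review (7.1) are N/A. Unscheduled visits (6.4) are left to staff judgement, and the one example is of someone still taking part. None of these forbids safety follow-up, but none provides a route for it after termination.

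**Scale.** Each terminated participant is 1/25 = 4% of the planned sample. That figure does not say how often an event would be open at termination. The protocol gives no termination rate, and the side-effect frequencies in 12.1 (headache about 25%, nausea about 5%) do not supply one.

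**The case against.** The best defence is context. Section 6.6 is headed as a section on visits and sits among others that say which visits take place. Read that way, its last sentence means only that no exit visit or battery of assessments is planned. Adverse events have their own chapter, which already contemplates withdrawal: 9.1.1 counts an abnormal diagnostic result as an adverse event if it leads to study withdrawal, and 9.2 reaches beyond the study period. A reader would ordinarily let specific safety rules prevail over a general sentence about visits. It can also be said that 6.6 speaks of study staff and 9.2 of the investigator, that 6.4 and 7.1 prohibit nothing, and that a wording problem of unknown frequency in a study the protocol calls minimal risk is a minor matter.

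Much of this is fair. The exit-assessment reading is reasonable and would remove the conflict; 6.4 and 7.1 are not prohibitions; the frequency is unknown. But 6.6 is unqualified, and its reader must supply the limit. Confining it to the termination contact does not help, because 9.2 applies at each contact. The staff/investigator distinction does not help either: 6.6 bars collection whoever does it, and 9.2 makes no exception for contacts made by staff. Nothing in the protocol states that section 9 prevails.

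**Conclusion.** The concern holds. As written, 6.6 conflicts with 9.2 under two of the three readings considered, and the text does not select the third. Under the literal reading, both follow-up duties for open events and the questioning at the termination contact are blocked, so far as they depend on the participant. Under the contact-only reading, only the questioning is blocked.

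The conclusion assumes that the termination contact counts as a contact under 9.2 and that the missing safety exception is not supplied elsewhere; none was found. Confidence is moderate because the sponsor may have meant only that there is no exit assessment. The number of participants affected cannot be estimated. Events that had already reached a 9.2 endpoint are untouched, as are all efficacy estimates and tests. It should be corrected because following 6.6 literally would lose safety information, and the correction is small.

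**What to change.** Reconcile 6.6 with 9.2 and 9.4.1:

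- Limit the last sentence of 6.6 to study outcome assessments.
- State in 6.6, or in 6.5.1 in place of N/A, that adverse-event questioning at the termination contact, and follow-up and reporting under 9.2 and 9.4.1, continue to apply to terminated participants, subject to a participant's right to decline further contact.

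If the sponsor meant only that no exit assessment takes place, the same edit makes that explicit. It concerns the collection of safety data and sets no dose, treatment or stopping rule.

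The cost is one or two sentences of protocol wording. They should be checked against what the consent form says about data after termination, which is not in the copy reviewed.
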